## List of abbreviations

AD	Axial Diffusivity
CAV	Centre for Aging and Vitality, Newcastle University
CST	Cortico-spinal Tract
CRF	Case Report Form
СТО	Clinical Trial Officer
DTI	Diffusion Tensor Imaging
FA	Fractional Anisotropy
MD	Mean Diffusivity
MRI	Magnetic Resonance Imaging
NIHSS	National Institute of Health Stroke Score
PI	Principal Investigator
RA	Research Associate
RD	Radial Diffusivity
ROI	Region of Interest

 SINONIMS Protocol V1.0 24.09.18
 (Amendment 1.1 01/11/19)
 (Amendment 1.2 17/08/20)
 (Amendment 1.3 05/01/21)

 05/01/21)
 (Amendment 1.4 18/05/2021)
 IRAS ID 249942
 Page 3 of 24

# Summary

A common consequence of ischaemic stroke is the loss of limb function. This can lead to a stoke survivor being unable to continue to live an independent life. It would be beneficial to stroke survivors if clinicians could accurately predict recovery of limb function. An accurate prognosis would also enable treatment plans such as the content and duration of rehabilitation to be optimised. However, at present there is a lack of reliable methods for predicting recovery of movement after stroke.

Advanced magnetic resonance imaging (MRI) imaging can demonstrate the effect of stroke on the nerve pathways in the brain and the changes in the affected muscles in great detail. Advanced MRI has shown early promise in making recovery predictions in small-scale studies. Our research aims to build on this evidence and answer the question of whether advanced MRI can be used to predict how well stroke survivors will recover lower limb function.

We aim to study 30 participants who have had a first ever ischaemic stroke within the previous one to four weeks causing different degrees of stroke severity affecting the lower limb. They will undergo MRI brain and lower limb muscle scans lasting 40-45mins in a dedicated MRI facility in Newcastle University's Campus for Ageing and Vitality or in the Neuroradiology department, Royal Victoria Infirmary, Newcastle-upon-Tyne. A test of physical strength and functional ability of the affected leg lasting about 30mins will be done by a member of the research team around the time of the MRI scan and repeated 3 months after stroke. Analysis of our findings will determine whether advanced MRI scan findings are linked to the stroke survivors' recovery of limb function.

SINONIMS Protocol V1.0 24.09.18 (Amendment 1.1 01/11/19) (Amendment 1.2 17/08/20) (Amendment 1.3 05/01/21) (Amendment 1.4 18/05/2021) IRAS ID 249942 Page 5 of 24

# **Background information**

Stroke is one of the most important contributors to loss of independence, frailty and multi-morbidity in the elderly. Long-term motor impairment is the most frequent consequence of stroke with 50% of patients suffering from hemiparesis and 30% being unable to walk without assistance (1). Appropriate and targeted rehabilitation is the key in improving the outcome of stroke survivors. This is currently hampered by the fact that there is no accurate or widely accepted early prognostic tool to predict stroke recovery. A number of attempts have been made to use advanced imaging with or without clinical parameters to develop accurate biomarkers for recovery. For example the PREP algorithm for upper limb recovery uses a combination of clinical (SAFE or Shoulder Abduction Finger Extension score), neurophysiological (TMS or Transcranial Magnetic Stimulation) and imaging biomarkers (DTI or Diffusion Tensor Imaging) to predict upper limb outcome (2) with moderate accuracy. However there is no such tool available for lower limb motor recovery, even though improved mobility is key to a stroke survivor being able to live independently.

Eighty percent of strokes are caused by cerebral infarction, also called ischaemic strokes. After ischaemic stroke in particular, there are a number of micro-structural effects on the brain such as disconnection of white matter pathways, dieback of these pathways distant from the site of damage (i.e. Wallerian degeneration) and loss of functional networks. Advanced MRI techniques can now measure these effects on brain tissue in detail. Most of the available evidence centres on integrity of cortico-spinal tracts as measured by diffusion tensor imaging (DTI). Restriction to water diffusion by the interaction with the cell structure means diffusion is higher along the direction of an axon/tract than across it. This orientational restriction is quantified by the degree of diffusion anisotropy. Loss of integrity of white matter pathways due to Wallerian degeneration after stroke causes change in anisotropy which is measured by certain MRI metrics, the commonest of which is fractional anisotropy (FA). A good correlation was demonstrated between fractional anisotropy in pons 30 days after stroke and subsequent motor outcome in a single-centre observational study (3). Therefore the advancement of imaging techniques raises the possibility that radiological data could now act as a biomarker for outcome, but the ideal combination of information is unclear.

Although brain is the primary organ affected in stroke, skeletal muscle is the main end-organ accountable for motor disability. Sarcopenia or loss of quality and quantity of muscle associated with increasing age and is an important contributor to frailty and multi-morbidity in this population. Stroke is also an important contributor to muscle condition and mass, which interacts with sarcopenia and in combination they both impact upon the recovery process and the outcome of patients. Greater understanding of the structural, metabolic and functional characteristics of sarcopenia in a disease-specific setting such as stroke, could enhance our understanding of sarcopenia in general as well as stroke recovery.

While a lot of attention has been paid to the brain injury and neurological consequences of stroke, relatively less research has focussed upon the structural, metabolic and functional aspect of the affected muscles. Stroke-related sarcopenia is not recognised in current guidelines for stroke

SINONIMS Protocol V1.0 24.09.18 (Amendment 1.1 01/11/19) (Amendment 1.2 17/08/20) (Amendment 1.3 05/01/21) (Amendment 1.4 18/05/2021) IRAS ID 249942 Page 6 of 24

therapy and rehabilitation. According to a systematic review, the evidence base for stroke-related sarcopenia comprises of 490 patients from 14 studies (including one UK study), which is miniscule compared to the body of evidence available for stroke in general (4). Only one of the studies included MRI imaging, where it was used to measure cross-sectional area of the arm (5). To our knowledge there is no MRI study which looks at lower limb muscle quality and quantity in early post-stroke setting.

Structural adaptive changes in muscle tissue have been observed to start as early as four hours after cerebral infarction which may be related to disrupted synaptic transmission of muscle innervating motor neurons which then leads to a reduction in motor units (6). A number of mechanisms influence the quantity and quality of the muscle tissue affected by stroke e.g. reinnervation, fibre-type shift, disuse atrophy and local inflammation (7). This inter-individual variability of end-organ changes in skeletal muscles, some of which may reflect other processes pre-stroke, could contribute towards the variability in outcomes after rehabilitation. Therefore a combined study of connectivity changes in brain after stroke together with changes in affected muscles may result in a prognostic tool for motor outcome and ultimately help individualise rehabilitation therapy e.g. neurological recovery may require greater cognitive engagement during rehabilitation activities or repair of interrupted pathways with stem cell therapy, whereas a patient with indicators for a relatively poor "muscle prognosis" may benefit from more intensive exercise practice to improve conditioning. Newcastle University is at the forefront of imaging of skeletal muscles and there is significant interest and expertise in gualitative and guantitative methodologies of assessing skeletal muscles in different disease processes (8). The ability of multi-modality MRI to assess the underlying pathophysiological process in sarcopenia has also been established by other research groups (9).

In summary, stroke-related sarcopenia and lower limb motor recovery are relatively underresearched areas in post-stroke setting. In addition, despite promising early imaging evidence from imaging studies, accurate early biomarkers of stroke recovery have not been fully developed and evaluated. The purpose of this research is to address the gap in research by: a) using advanced imaging to study structural, metabolic and functional characteristics of lower limb muscles in poststroke setting b) addressing the translational gap between early evidence of MRI biomarkers for motor recovery in brain and muscles and their potential use after ischaemic stroke by developing biomarkers for predicting lower limb motor recovery and c) widening our understanding of sarcopenia in general and thereby help prevent frailty and multi-morbidity in elderly population.

## Aim

To study the association and interaction between motor outcomes and advanced MRI biomarkers in the brain and affected lower limb muscles after first ever ischaemic stroke.

# **Objectives**

• To describe the relationship between stroke-related sarcopenia with loss of connectivity in the brain

SINONIMS Protocol V1.0 24.09.18 (Amendment 1.1 01/11/19) (Amendment 1.2 17/08/20) (Amendment 1.3 05/01/21) (Amendment 1.4 18/05/2021) IRAS ID 249942 Page 7 of 24

- To describe the relative strengths of correlation of individual muscle and brain imaging biomarkers to motor outcome (as determined by lower limb Fugl-Meyer score, lower limb motor NIHSS and dynamometry measurement) compared to that of a combination of imaging biomarkers to motor outcome
- To develop a predictive model of motor outcome at 3 months based on brain and muscle biomarkers obtained 1-4 weeks after stroke
- To establish the feasibility of obtaining simultaneous brain and muscle MRI imaging relatively early after stroke by description of recruitment rate, drop-out rate and rate of incomplete and sub-optimal imaging
- To obtain data to inform the design and sample size required for a blinded observational study to confirm the operational characteristics of an algorithm using baseline advanced MRI biomarkers of neurological injury and sarcopenia to predict motor outcome.

# Study setting

Potential participants will be identified and recruited from two NHS stroke services in North East England. Patients will undergo a MRI study at 1-4 weeks following onset of symptoms of stroke. The MRI study will be carried out in Magnetic Resonance Centre at the Campus of Aging and Vitality, Newcastle University or in the Neuroradiology department, Royal Victoria Infirmary, Newcastle-upon-Tyne.

# **Study population**

Inclusion criteria:

- a) Adults aged 18 or over with first ever unilateral supra-tentorial ischaemic stroke.
- b) Unilateral lower limb motor deficit +/- upper limb motor deficit.
- c) Less than 4 weeks after stroke onset.

Exclusion criteria:

- a) Absolute contra-indication to MRI (e.g. pacemaker).
- b) **Posterior circulation Cerebellar stroke** or haemorrhagic stroke (haemorrhagic transformation of ischaemic stroke is not considered as an exclusion criterion).
- c) Previous history of anterior circulation stroke (clinically or radiologically) or posterior circulation stroke with residual clinical deficit.
- d) Lack of capacity to provide informed consent.
- e) Unable to transfer independently or with assistance of one person if scanned in Newcastle University or with assistance of two people if scanned in Royal Victoria Infirmary. Unable to transfer with the assistance of two people for patients scanned in Newcastle University.
- f) Unable to answer MRI safety questionnaire.

SINONIMS Protocol V1.0 24.09.18 (Amendment 1.1 01/11/19) (Amendment 1.2 17/08/20) (Amendment 1.3 05/01/21) (Amendment 1.4 18/05/2021) IRAS ID 249942 Page **8** of **24** 

- g) Moderate to high level of dependency prior to stroke (modified Rankin score of >2).
- h) Any other pre-existing co-morbidity causing a significant lower limb deficit.

i) Hip or knee replacement of either lower limb.

NB. Patients requiring a hoist for transfer will not be considered a contra-indication if scanned in RVI although it will be a contra-indication for patients scanned in Newcastle University.

Recruitment will cease once 30 patients have attended for MRI studies. If a patient attends for but is unable to tolerate/complete the MRI study then he/she will continue to be in the study and be part of the feasibility analysis. If a patient is enrolled in the study but does not attend the MRI study, then the clinical assessment (s) if undertaken will be reported. Such a patient will be replaced by

SINONIMS Protocol V1.0 24.09.18 (Amendment 1.1 01/11/19) (Amendment 1.2 17/08/20) (Amendment 1.3 05/01/21) (Amendment 1.4 18/05/2021) IRAS ID 249942 Page 9 of 24

another patient willing to undergo MRI so that the total number of 30 patients attending for MRI is achieved.

## Data collection

After informed consent is obtained the following baseline demographic and clinical data will be recorded:

- Patient demographics (age, sex; handedness)
- Date of onset of stroke symptoms
- Pre-morbid modified Rankin score
- Pre-morbid walking status (independent or not)
- Associated co-morbidities e.g. presence of diabetes, hypertension, arthritis of affected limb.
- Stroke treatment (thrombolysis/thrombectomy).

Following this, two structured clinical assessments will be undertaken as follows:

#### Baseline clinical assessment:

Clinical assessment will be completed by a trained observer who will be blinded to the MRI data. This will take approx. 30 mins. It will be undertaken on the day of the MRI study if possible to minimise the number of times the patient has to travel. If this is not feasible or if the patient is unable to have both imaging and clinical assessment on the same day due to their physical condition, then this will be arranged within a week of the MRI study. If done on the same day, the clinical assessment will be undertaken at a dedicated facility at the Magnetic Resonance Centre, Newcastle University, or in the Department of Stroke Medicine, Ward 41, Royal Victoria Infirmary, Newcastle-upon-Tyne.

Following data will be collected during the baseline clinical assessment:

• Lower limb Fugl-Meyer score (Appendix 2, 10min)

SINONIMS Protocol V1.0 24.09.18 (Amendment 1.1 01/11/19) (Amendment 1.2 17/08/20) (Amendment 1.3 05/01/21) (Amendment 1.4 18/05/2021) IRAS ID 249942 Page 10 of 24

- Lower limb motor NIHSS score (Appendix 3, 10min)
- Lower limb dynamometry (Appendix 4, 5min)
- Functional ambulatory score (Appendix 5, 5min).

#### Follow-up clinical assessment

A single follow up assessment of motor recovery will take place in Magnetic Resonance Centre in Newcastle University. This will take place three months +/- 7 days after the onset of stroke. The follow-up period can be extended to 6 months for a limited number of patients under exceptional circumstances. The following assessments will be undertaken:

- Lower limb Fugl-Meyer score (10min)
- Lower limb motor NIHSS score (10min)
- Lower limb dynamometry (5min)
- Functional ambulatory score (5min).

The study timelines are detailed in Appendix 6.

## Planned advanced MRI imaging

A 3 Tesla MRI study will take place in the Magnetic Resonance Imaging Centre in Centre for Aging and Vitality (CAV) in Newcastle University or in the Neuroradiology department, Royal Victoria Infirmary, Newcastle-upon-Tyne. The research team will liaise with the participant (or the relevant clinical team if still in hospital) and the MRI team to pre-book an appointment. The study will take approximately 45-50 min. Travel and parking costs for the participants will be re-imbursed from the study budget.

The CTO/member of the clinical team at the recruiting site will undertake an initial MRI safety screening (for absolute contraindications e.g. cardiac pacemaker) before obtaining permission to pass on the patient's details to the research associate. A member of the research team will subsequently undertake additional screening for MRI safety at the time of booking the MRI study. A member of the MRI team will undertake a final MRI safety screening with the patient on the day immediately before the study is undertaken. Any instance of study being cancelled due to MRI safety concern will be documented and reported alongside study results.

The following MRI sequences will be performed (Appendix 7):

1. Brain imaging: Structural - 3D volume T1; Functional imaging: DTI (approx. 15 min).

SINONIMS Protocol V1.0 24.09.18 (Amendment 1.1 01/11/19) (Amendment 1.2 17/08/20) (Amendment 1.3 05/01/21) (Amendment 1.4 18/05/2021) IRAS ID 249942 Page 11 of 24

2. Muscle imaging: 3D volume T1, STIR, 3 point Dixon or equivalent, MR spectroscopy of the thigh muscles (approx. 25-30 min).

The images will be transferred to a workstation for review by an observer who will be blinded to the clinical status of the patient. Following assessments will be made on the structural brain imaging: lesion location, lesion side, lesion number, lesion volume, anatomical structures involved, vascular territory involved, any other pathology.

The following quantitative assessments will be made from the functional brain imaging sequences: DTI imaging – a region of interest will be drawn on the pyramidal tracts at the level of mid-brain and internal capsule and the following parameter will be measured: FA, relative FA (i.e. FA ratio between normal and abnormal sides) and axial, radial and mean diffusivity.

The following assessments will be made from the muscle MRI:

- a) Muscle volume, based on a 6 point scale described by Mercuri et al (10)
- b) Muscle oedema, based on a 4 point scale (absent, mild, moderate, severe)
- c) Fatty infiltration, based on 3 point Dixon method or equivalent (8)
- d) Intra-myocellular lipid content on MR spectroscopy.

## Image data

The following data will be extracted from the cranial MRI studies:

- Site of infarction location will be anatomically classified as frontal, parietal, temporal, occipital, basal ganglia; it will also be classified along vascular territories e.g. middle cerebral artery, anterior cerebral artery or posterior cerebral artery, etc
- Side of infarction
- Infarct volume region of interest (ROI) will be placed on the affected region and volume will be measured using validated software
- Cross-sectional DTI measurements axial, radial and mean diffusivity (AD, RD and MD), fractional anisotropy (FA) (ROIs will be placed in the cortico-spinal tracts on both sides at the levels of corona radiata, internal capsule and cerebral peduncle).
- Whole tract DTI measurement 3D Tractographic analysis of the whole cortico-spinal tract on both sides will be made with measurements of whole tract volume, MD and FA.

The following data will be extracted from the muscle MRI studies:

• Muscle volume – this will be performed on the T1 volume data based on a 6 point scale described by Mercuri et al. The volume of the whole thigh and that of the largest thigh muscle (vastus lateralis) will be measured.

SINONIMS Protocol V1.0 24.09.18 (Amendment 1.1 01/11/19) (Amendment 1.2 17/08/20) (Amendment 1.3 05/01/21) (Amendment 1.4 18/05/2021) IRAS ID 249942 Page 12 of 24

- Fat fraction analysis this will be done using the fat only images obtained from 3 point Dixon method.
- Intra-myocellular lipid content MR spectroscopy will be performed on the Vastus Lateralis muscle on both sides. Intra-myocellular lipid fraction will be obtained by interrogating the two lipid peaks seen on the MR spectrum.
- Muscle oedema this will be obtained from the STIR sequence based on a 4 point scale (absent, mild, moderate, severe).

All measurements will be made in the affected and normal sides and a ratio of parameters between the two sides will be calculated.

## Data storage

Paper CRFs will be transferred in a secure manner by the study RA from the recruiting site to Newcastle University. The original CRFs will be stored securely in a locked safe in the Stroke Research Centre at Newcastle University. The consent forms will be filed in the patient notes.

Clinical data will be entered into a database by the study RA which will then be stored securely on a Newcastle University server. Imaging data will be stored securely in the space allocated to Magnetic Resonance Centre in the Newcastle University data store. The research team will comply with the data protection requirements as set out in Good Medical Practice guidelines, by the study sponsor and the Data Protection Act.

# Data analysis

In order to effectively explore this research question, two hypotheses are proposed:

*Hypothesis A*: Sarcopenia and loss of motor impairment will be most pronounced in those patients whose ischaemic stroke causes greatest damage to the cortico-spinal (CS) tract and motor pathways as determined by advanced neuroimaging.

*Hypothesis B*: A combination of imaging biomarkers of loss of connectivity in brain and sarcopenia will increase the ability to predict motor outcome in stroke when compared to individual biomarkers alone.

In line with the study hypotheses the following broad categories of analyses will be undertaken.

SINONIMS Protocol V1.0 24.09.18 (Amendment 1.1 01/11/19) (Amendment 1.2 17/08/20) (Amendment 1.3 05/01/21) (Amendment 1.4 18/05/2021) IRAS ID 249942 Page 13 of 24

*Analysis* A: Degree of sarcopenia (as determined by study of muscle volume, fat fraction and oedema on MRI) will be used as a covariate in a regression analysis between motor outcome (lower limb Fugl-Meyer score) and neuroimaging assessment of CS tract integrity (fractional anisotropy or FA as determined from diffusion tensor imaging or DTI).

*Analysis B*: Correlation of a combined biomarker of brain connectivity and sarcopenia versus motor outcome (as determined by lower limb Fugl-Meyer score) will be stronger than correlation between individual biomarkers and motor outcome.

The following individual statistical analyses will be performed:

- Correlation between cortico-spinal tract (CST) DTI data (AD, RD, MD and FA of cross sectional data and MD and FA of 3D tractographic data) and muscle MRI data (volume, fat fraction, intra-myocellular lipid fraction and muscle oedema)
- Correlation between CST DTI data and lower limb Fugl-Meyer score, motor NIHSS and dynamometry measurement at 3 months
- Correlation between CST DTI data and change in Fugl-Meyer score, motor NIHSS and dynamometry measurement between baseline and 3 months
- Correlation between muscle MRI data and Fugl-Meyer, motor NIHSS and dynamometry measurement score at 3 months
- Correlation between muscle MRI data and change in Fugl-Meyer score, motor NIHSS and dynamometry measurement between baseline and 3 months
- Correlation between combined CST DTI/muscle MRI data and lower limb Fugl-Meyer score at 3 months
- Correlation between combined CST DTI/muscle MRI data and change in lower limb Fugl-Meyer score between baseline and 3 months
- Multi-variate regression analysis of muscle and cranial DTI data and lower limb Fugl-Meyer scores.

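### Hypothesis B rests on a bare stronger correlation for an undefined combined biomarker; if its weights are fitted to the same 30 or fewer patients, the comparison cannot show that combining adds nothing

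*Protocol*

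**What the plan says.** Hypothesis B (Protocol, Data analysis) holds that combining imaging markers of brain connectivity and sarcopenia "will increase the ability to predict motor outcome in stroke when compared to individual biomarkers alone". Analysis B, which answers it, is worded as an expected result: "Correlation of a combined biomarker of brain connectivity and sarcopenia versus motor outcome", measured by the lower limb Fugl-Meyer score, "will be stronger than correlation between individual biomarkers and motor outcome".

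The list of individual analyses includes "Correlation between combined CST DTI/muscle MRI data and lower limb Fugl-Meyer score at 3 months" and the same for change from baseline. A separate last item is "Multi-variate regression analysis of muscle and cranial DTI data and lower limb Fugl-Meyer scores". Nothing ties that regression to the combined biomarker. One of the Objectives is "To develop a predictive model of motor outcome at 3 months based on brain and muscle biomarkers obtained 1-4 weeks after stroke".

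Recruitment stops at 30 patients attending for MRI. Attenders who cannot complete the scan stay in the study and count towards the 30 (Case ascertainment, consent and recruitment), so the biomarker analyses may have fewer.

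The DTI components are described in two ways. Under Planned advanced MRI imaging, "a region of interest will be drawn on the pyramidal tracts at the level of mid-brain and internal capsule". Under Image data, regions are placed "at the levels of corona radiata, internal capsule and cerebral peduncle", whole-tract measures are added, and side-to-side ratios are calculated.

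**The concern.** Analysis B compares apparent correlations within one set of patients. If the combined biomarker is a weighted sum whose weights come from regressing the outcome on the markers in those patients, its correlation with the outcome is at least that of every component, even when the added markers carry no information. A stronger correlation then shows only that more terms were fitted.

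Two things are at stake. One of the study's two hypotheses could appear supported when combining markers adds nothing. The Objectives also say that the data are to inform the design and sample size of a later blinded study; an uncorrected R taken from a fitted combination would be too optimistic for that use.

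**Working it through.** **Plan's own figure.** There is none to reproduce. The Protocol states no effect size, alpha or power, and says that no formal sample size calculation was done.

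**Inputs.** From the Protocol: at most 30 patients with MRI, and FA plus muscle measures as components. Analysis A uses FA with three sarcopenia features (volume, fat fraction, oedema), which corresponds to the three-marker row below. Assumed: true FA-outcome correlation 0.5, independent normal markers, and muscle markers unrelated to outcome, so that the combination truly adds nothing. A smaller analysable number of 24 was also tried, again as an assumption.

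**Algebra.** For two markers with sample correlations r1 and r2 with the outcome, and r12 with each other, least-squares weights give

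R² = r1² + (r2 − r1·r12)² / (1 − r12²).

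The added term is a square over a positive number, so R² ≥ r1²; by symmetry R² ≥ r2². For example, r1 = 0.5, r2 = 0 and r12 = 0.2 give 0.25 + 0.01/0.96 = 0.260, so R = 0.51. A second marker with zero correlation with outcome still raises R.

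**Expected size.** After an intercept and FA, each noise marker takes on average 1/(n − 2) of the remaining variation. With n = 30 and r1² ≈ 0.25, R² is about 0.25 + 0.75·q/28 for q noise markers:
- q = 1: 0.277, R ≈ 0.53
- q = 3: 0.330, R ≈ 0.57
- q = 5: 0.384, R ≈ 0.62

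**Simulation** (n = 30, 4,000 to 5,000 runs per setting). FA alone averages 0.49 and the best single marker about 0.50.

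| Noise markers added | Mean R, fitted | Fitted combination stronger than best single marker | Unweighted sum stronger than best single marker | Lower leave-one-out error than FA alone | Nested F test, p < 0.05 |
|---|---|---|---|---|---|
| 1 | 0.52 | 100% | 12% | 17-18% | 5% |
| 3 | 0.57 | 100% | 6% | 13% | 5% |
| 5 | 0.62 | 100% | 4% | 8-9% | 5% |

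The gain over FA alone was at least 0.05 in 18%, 58% and 84% of runs. With 24 patients the mean R is 0.53, 0.59 and 0.65.

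**Reading.** With fitted weights the criterion is met in every run. With a fixed equal-weight sum it usually fails when the extra markers are noise, so the defect depends on fitting. A mere improvement in leave-one-out error is not a sufficient rule either: it accepts one noise marker in about 17-18% of runs, whereas the nested F test holds its nominal 5%.

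**The case against.** The strongest objection is that the Protocol never says the weights are fitted. Correlation with the combined data and the regression are separate items, and a score fixed in advance would be a legitimate reading. This stands. A reader might infer that Analysis B can never fail; the documents support that only for fitted weights.

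Second, the construction of the composite and any internal validation may be in a SAP that is not shown. That also stands, and their absence is not the point here. The point is the criterion the Protocol does state, which would remain a bare comparison of strength in the same patients.

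Third, the study is early and observational, its aims are largely descriptive, and confirmation of an algorithm is left to a later study. This lowers the seriousness but does not make the comparison informative.

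Fourth, Analysis A already regresses Fugl-Meyer on FA with sarcopenia as a covariate, which is close to the fuller nested model. True, but the Protocol does not make it the test of Hypothesis B.

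Two further inferences should be resisted. A reader might enter every DTI and muscle measure into one model and quote the very high R-squared expected by chance; the Protocol commits to no such model. A reader might also take the differing lists of levels to mean that the best-correlating FA will be picked; nothing says so. The cerebral peduncle is part of the mid-brain, so the lists differ mainly in the corona radiata and the whole-tract values.

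**Conclusion.** The concern holds conditionally. Analysis B sets a poor criterion for Hypothesis B: stronger correlation in the same 30 or fewer patients, for a combination that is not defined. If the weights are fitted in those patients, the criterion is met by construction. In the simulated case R is inflated by roughly 0.03, 0.08 or 0.13 over FA alone for 1, 3 or 5 noise markers. That all fitted combinations win follows from algebra; the sizes rest on the assumed FA correlation of 0.5, independent markers and n = 30, and grow with fewer patients. If the combination is an unweighted score fixed in advance, this problem does not arise. Given the exploratory design and the planned later confirmation, this is worth correcting but does not invalidate the study.

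**What to change.** Replace the bare comparison in Analysis B with a nested-model comparison:

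1. Regress the 3-month Fugl-Meyer score on one pre-specified FA measure, then add one pre-specified sarcopenia measure.
2. Judge Hypothesis B by the F test for the increment in R-squared, or by a confidence interval for it.
3. Report leave-one-out or bootstrap optimism-corrected R-squared for both models as a supporting estimate, and use that value for the follow-on study's design. Do not make a rise in the corrected value the sole rule.
4. Reconcile the DTI levels under Planned advanced MRI imaging and Image data, so that the sponsor can name the single FA measure in advance, including its level and whether it is an absolute value or a side ratio.
5. Label all other combinations exploratory.

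The cost is a change of wording and slightly more analysis work, with no new data. The reported gain from combining biomarkers will probably look smaller.
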